## 1.9.4 Handling of missing values/censoring/discontinuations

#### For the analyses re-run during RW period

The loss of PASI 75 response during RW period will be re-run. The subjects who have no lost PASI 75 response during RW will be considered as censored observations. Subjects who have not lost PASI 75 response but with missing values during RW will be considered as censored at prior available visit. Subjects who administered psoriasis concomitant medication (as per [MAP Appendix]), will be considered as failures at time of first administration if this occurred before the loss of PASI 75. Subjects who did not have PASI 75 response but randomized in RW period will be censored at day 0. Subjects with missing values at week X (X <156) and who have not lost PASI 75 response earlier, will be censored at week X (if they have not dropped out due to lack of efficacy or not administered psoriasis concomitant medication). Subjects who drop-out due to lack of efficacy will be considered as failure at time of drop-out. If drop-out was due to other reason, subjects will be considered as censored at time of drop-out. Intermediate missing values will not be considered.

Other time-to-event analyses will be handled analogously. For imputation techniques, please refer to Table 1-16.

For other analyses (not time to event) missing values with respect to response variables based on PASI score and IGA mod 2011 score will be imputed with multiple imputation regardless of the reason for missing data (e.g., premature study discontinuation, missed visit, administrative issues).

Following the intent-to-treat principle for subjects who prematurely discontinue treatment, but who are observed in the follow-up period, efficacy data collected in follow-up periods will be linked to planned but missed study visits as well, following imputation schemes described in Sections 1.5.4.1 and 1.9.4.2. (e.g., if a subject discontinues treatment at Week 56, but has follow-up visit F4, the PASI score observed at Visit F4 might be used for Week 60 assessments).

Novartis	Confidential	Page 39
RAP Module 3	9-Apr-2018 (1:15)	Secukinumab / AIN457A2302E1

For rebound and relapse no imputed data will be used and analyses will be based on observed data only.

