# 1.9.4.1 Details for imputations (non- responder and LOCF) and visit windowing

Note: These details are not applicable to time to event analysis. Only PASI and IGA mod 2011 based response variables are imputed with non-response, other response variables (e.g. for HAQ-DI, EQ-5D, DLQI) will be imputed with LOCF. Baseline values will not be carried forward. If all post baseline values are missing for one efficacy parameter, then these missing values will not be imputed and this subject will be removed from the analysis of the corresponding variable.

- Non- responder imputation for subjects with PASI 75 response at Week 52 RW period (Week 52 up to Week 156)
  - 1. Assign period to each visit as per CRF visit (CRF period) or as per visit date for unscheduled visits (analysis period)
  - 2. Assign analysis visit windows (for RW period from week 52 up to Week 156) according to Section 1.5.4. Of note, RW CRF period visits will not be assigned to treatment analysis period, whereas follow-up period CRF visits might be assigned to RW analysis period for subjects who do not enter treatment CRF period)
  - 3. If no CRF visit is assigned to an analysis visit as per Section 1.5.4, impute non-response

Note – Subjects with PASI 75 response at week 52 enter RW period. RW period is not fixed for all the subjects but varies for subject to subject based on occurrence of relapse. Subjects in RW period will enter treatment period only after first full relapse, if it occurs; otherwise not. Partial responders are not entering the RW period but go into the treatment period.

- LOCF imputation
- 1. Assign period to each visit as per CRF visit (CRF period) or as per visit date for unscheduled visits (analysis period)
- 2. Assign analysis visit windows (for RW period from week 52 up to Week 156) according to Section 1.5.4. Of note, RW CRF period visits will not be assigned to treatment analysis period, whereas follow-up CRF period visits might be assigned to RW analysis period for subjects who do not enter treatment CRF period)
- 3. If no CRF visit is assigned to an analysis visit as per Section 1.5.4, impute with LOCF

Note: All data collected in the eCRF will be considered for LOCF imputation regardless of whether the data was considered in analysis visit windows.

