## 1.9.4.2 Multiple imputations

Loss of PASI 75 response will be evaluated as described above in section 1.9.2 with multiple imputations instead of non-responder imputation for missing values. Multiple imputation will also be used for PASI/IGA score and responses variables.

Novartis	Confidential	Page 41
RAP Module 3	9-Apr-2018 (1:15)	Secukinumab / AIN457A2302E1

Multiple imputation (MI) is a simulation based approach where missing values are replaced by multiple Bayesian draws from the conditional distribution of missing data given the observed data and covariates, creating multiple completed data sets. These completed data sets can then be analyzed using standard methods. Rubin (1987) presented rules how to combine the multiple sets of estimates to produce overall estimates and confidence intervals that adequately incorporate missing data uncertainty.

Missing values for the 'change from baseline PASI score' will be imputed based on an underlying normal distribution and using a Markov Chain Monte Carlo (MCMC) method. The change from baseline in PASI score appears to follow closer to a normal distribution than the actual PASI score.

The imputations will be done separately for each treatment group including baseline weight, failure to at least one previous biologic (yes/no), and number of previous systemic therapies as additional covariates. Values post assessment timepoint of the primary endpoint will not be considered for imputations.

The number of imputations will be set to 100, the seed for the random function will be set to 457230201 for this study. To generate the multiple imputed data sets, the SAS procedure MI can be used as follows:

The input data set <pasi> should have one record per subject with baseline PASI as well as all changes from baseline PASI score.

ODS LISTING CLOSE;

PROC MI DATA=<pasi> OUT=<impdata> SEED=457230201 NIMPUTE=100; EM maxiter=300; VAR <baseline weight> <failure to at least one biologic> <number of previous systemic therapies> <baseline PASI> <change from baseline PASI week 52> <change from baseline PASI week 56> <change from baseline PASI week 60> <change from baseline PASI week 64> <change from baseline PASI week 64> <change from baseline PASI week 68> BY <treatment group>; RUN;

ODS LISTING;

Novartis	Confidential	Page 42
RAP Module 3	9-Apr-2018 (1:15)	Secukinumab / AIN457A2302E1

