The imputed data are saved in data set <impdata>. The outcomes of interest, i.e. the loss of PASI 75 response will be calculated from change from baseline PASI scores. The day of visit at which the first occurrence of losing PASI 75 response will also be obtained. In the case of missing visits or visit dates the planned visit day will be used., e.g. as follows:

DATA <impdata2>; SET <impdata>; IF <change from baseline PASI week primary endpoint>/<baseline PASI>=0.75 THEN <PASI 75 response>=1; ELSE <PASI 75 response>=0; END; RUN;

The treatment differences for each imputed data set will then be evaluated by using Cox proportional hazards regression as described section 1.9.2. This analysis will be done by \_IMPUTATION\_ for each pairwise comparison as described in section 1.9.5. The data set should be sorted such that the control group comes last. E.g as follows:

```
ods table HazardRatios = hazardratios
proc phreg data = <impdata2>;
class <treatment group> <core study> <geographical region> <body weight stratum>
model TIME*PASI75(1)= <treatment group> <core study> <core baseline PASI> <extension baseline PASI>/ties=exact;
STRATA < geographical region> < body weight stratum>
by _Imputation ;
run:
      data dhazardratios:
            set hazardratios;
            where Description in ( 'TRT01PN 1 vs 3' 'TRT01PN 2 vs 4');
            if Description in ( 'TRT01PN 1 vs 3') then comp =1;
            else if Description in ('TRT01PN 2 vs 4') then comp =2;
            if HazardRatio NE . and HazardRatio > 0 then ESTIMATE=log(HazardRatio);
            if WaldLower NE . and HazardRatio > 0 then STDERR=log(WaldLower/HazardRatio)/-probit(1-0.05/2);
            if missing(ESTIMATE) or missing(STDERR) then delete;
     effect="LogHR";
      run;
```

• The PHREG procedure and following MIANALYZE procedure could then be run with by-variables for the comparison and response identifier.

The MIANALYZE procedure expects the parameter estimate in the variables ESTIMATE, and the corresponding standard error in the variable STDERR. The dataset dhazardratios above contained the estimate and its standard error for log(Hazard ratio)

The estimates and standard errors of the log of hazard ratio based on the 100 imputed data are then combined by applying Rubin's rules for multiple imputed data sets, see Little and Rubin (2002).

The SAS procedure MIANALYZE will be applied as follows:

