## Steps for Cumulative Probabilities and CIs:

- 1. Create 100 imputed datasets including time to loss of PASI 75 response for each patient using PROC MI.
- 2. Run PROC LIFETEST for each imputed data set and store estimates for the survivor function (SURVIVAL) and the associated standard errors (STDERR) in the data set OUTSURV.

run;

- 3. In a data step use the data set OUTSURV to calculate
  - 1. T SURVIVAL=log(-log(SURVIVAL))
  - 2. T\_STDERR= STDERR/(SURVIVAL\*log(SURVIVAL))

data outsurv1; set outsurv;

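### SAP 1.9.4.2: the multiple-imputation analysis of loss of PASI 75 does not keep rule-based failures as events, so it changes the event definition as well as the missing-data handling

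*SAP*

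**What the plan says.** **Main time-to-event rules.** SAP 1.9.4 (re-run analyses in the randomized withdrawal period) covers three groups:

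- Psoriasis medication: "Subjects who administered psoriasis concomitant medication (as per [MAP Appendix]), will be considered as failures at time of first administration", provided this comes before loss of PASI 75.
- Lack of efficacy: "Subjects who drop-out due to lack of efficacy will be considered as failure at time of drop-out".
- Other reasons: "If drop-out was due to other reason, subjects will be considered as censored at time of drop-out".

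Table 1-14 (SAP 1.9.7) also makes psoriasis medication an event for this variable. It lists discontinuation for lack of efficacy in its informative-censoring column and restricts the PASI-based event to observed loss, without imputation.

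**MI analysis.** SAP 1.9.4.2 opens with: "Loss of PASI 75 response will be evaluated as described above in section 1.9.2 with multiple imputations instead of non-responder imputation for missing values". It imputes change from baseline in PASI by treatment group and derives the outcome thus: "The outcomes of interest, i.e. the loss of PASI 75 response will be calculated from change from baseline PASI scores". For the cumulative probabilities and for the log-rank and Wilcoxon p-values, the first step is: "Create 100 imputed datasets including time to loss of PASI 75 response for each patient using PROC MI". No step or code line uses medication or the reason for drop-out.

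**Non-responder imputation.** SAP 1.9.4.1, which sets it out, begins: "Note: These details are not applicable to time to event analysis".

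**The concern.** A missing-data sensitivity analysis should vary the assumption about unobserved values and hold the endpoint fixed. If no data were missing, it should reproduce the main analysis. As written, this one need not, because some subjects who are failures under 1.9.4 can be non-losers under 1.9.4.2.

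MI is the only missing-data sensitivity analysis that the SAP itself specifies for loss of PASI 75. If its hazard ratio differs from the main one, a reader would naturally conclude that missing data matter. If the two agree, the reader would conclude that they do not. Neither inference is safe when the event definition moves at the same time.

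**Working it through.** **1. The plan's own figure.** Inputs from SAP 1.11: 276 subjects on 150 mg, 138 on placebo, 10% versus 23% losing PASI 75, one-sided 2.5%, power above 90% with about 400 subjects.

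- HR = ln(0.90)/ln(0.77) = 0.403.
- Events = 276 × 0.10 + 138 × 0.23 = 27.6 + 31.7 = 59.3.
- Schoenfeld: z = |ln 0.403| × √(59.3 × 2/3 × 1/3) − 1.960 = 1.34, power 91%.
- Freedman: z = (1 − 0.403) × √(2 × 59.3)/(1 + 2 × 0.403) − 1.960 = 1.64, power 95%.
- With 267/133 the two give 90.0% and 94.3%.

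The stated power is reproduced. It is only the starting point for step 4.

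**2. The rules side by side.**

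| Subject still holding PASI 75 | Main analysis (1.9.4) | MI as written (1.9.4.2) |
|---|---|---|
| Takes psoriasis medication | Event at first administration | Event only if observed or imputed PASI shows loss |
| Drops out for lack of efficacy | Event at drop-out | Later PASI imputed; event only if a draw shows loss |
| Drops out for another reason | Censored | Later PASI imputed |

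The first row is a change of endpoint. The third is a change of missing-data handling. The second is partly each. Anyone whose observed PASI already shows loss is an event in both analyses.

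**3. Two constructed subjects.**

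*Medication user.* The last dose is at Week 56, psoriasis medication follows, and study treatment stops. Protocol 5.5.9 then asks for the end-of-treatment visit about four weeks after the last dose, followed by the two follow-up visits, which is about Weeks 60, 64 and 68. SAP 1.9.4 allows follow-up efficacy data to stand in for missed visits. If improvement is at least 75% at all three, nothing is imputed. The main analysis records a failure; MI records no loss. Because 1.9.4.2 takes in all PASI changes, these on-medication values also inform imputation for the rest of the arm.

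*Lack-of-efficacy drop-out still at PASI 75 at Week 60.* This uses a toy model, with every parameter assumed. Week 52 improvement is normal with mean 92% and SD 6, limited to 75-100. The fall per visit is 3 or 5 points, and the visit-to-visit SD is 4.8 or 7.2. Such a subject is a non-loser to Week 68 in 48-73% of draws, or 16-34% if Week 60 improvement was only 75-82%.

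**4. Effect on the hazard ratio.** Assume that the planned 10% and 23% include rule-based failures, and that a share f of failures in an arm becomes non-losers. Then HR′ = ln(1 − 0.10(1 − f_S))/ln(1 − 0.23(1 − f_P)), where S is secukinumab and P is placebo. The documents give no value for f; 10-30% is an assumed range.

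| Failures lost | f | Loss rates, S / P (%) | HR′ | Power, Schoenfeld |
|---|---|---|---|---|
| None | 0 | 10.0 / 23.0 | 0.403 | 91% |
| Both arms equally | 10% | 9.0 / 20.7 | 0.407 | 87% |
| | 20% | 8.0 / 18.4 | 0.410 | 83% |
| | 30% | 7.0 / 16.1 | 0.413 | 77% |
| Placebo only | 10% | 10.0 / 20.7 | 0.454 | 80% |
| | 20% | 10.0 / 18.4 | 0.518 | 62% |
| | 30% | 10.0 / 16.1 | 0.600 | 40% |
| Secukinumab only | 10% | 9.0 / 23.0 | 0.361 | 95% |
| | 20% | 8.0 / 23.0 | 0.319 | 98% |
| | 30% | 7.0 / 23.0 | 0.278 | 99% |

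On placebo, 10-30% of 31.7 failures is about 3 to 10 subjects. The power column describes the re-defined analysis under the planning assumptions; the trial's planned power is unaffected.

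**The case against.** **The SAP is silent, not contradictory.** Table 1-14 defines the variable itself, 1.9.4 says other time-to-event analyses are handled in the same way, and the MI code is offered as an example. A programmer could keep the rules. This stands in part. However, the carry-over sentence does not name MI, the table's PASI-based event excludes imputed values, and the specific section gives its own derivation. Followed literally, it drops the failures.

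**The protocol started it.** The protocol's primary analysis (9.4.2, 9.4.3) has no medication or lack-of-efficacy rule, and its MI analysis (9.4.4) also derives response from imputed scores. That is correct, and it places the mismatch between SAP 1.9.4 and SAP 1.9.4.2. It does not remove it, because the analysis that MI is compared with is the one in 1.9.4.

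**Few subjects may be affected.** Full relapse means losing more than half of the maximal improvement. Improvement is then below 50%, so every relapse is already a PASI 75 loss. Rescue medication is not permitted (Protocol 5.5.6). What counts as psoriasis medication is defined in an appendix that is not part of these documents. All of this stands: the number could be small.

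**Little rests on it.** The listed MI visits stop at Week 68, and the SAP does not repeat the Week 68 primary analysis. No confirmatory decision in this SAP depends on the result. This also stands.

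**Stronger readings that a reader might infer.**

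- *MI tests another endpoint and says nothing about missing data.* Not supported. Drop-outs for other reasons do move from censored to imputed, and the lack-of-efficacy rule is itself partly a censoring rule.
- *MI understates loss on placebo.* Not supported. This needs rule-based failures to be concentrated on placebo, and the documents give no counts by arm.
- *The non-responder analysis that MI is said to replace exists nowhere.* Too strong. Protocol 9.4.4 has a Cox analysis that classes such subjects as non-responders. Within the SAP, though, 1.9.4.1 rules non-responder imputation out for time-to-event analysis, so the comparison named in 1.9.4.2 is wrong there.

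**Conclusion.** The point holds in a limited form. As written, SAP 1.9.4.2 does not keep the 1.9.4 and Table 1-14 failures as events for subjects who still hold PASI 75. The event definition therefore changes together with the missing-data handling, clearly so for medication users. A difference between the MI and main hazard ratios cannot be attributed to missing data alone.

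Size and direction are open. From the planned 0.40, the hazard ratio barely moves (0.407-0.413) if equal shares are lost in both arms. It rises to 0.45-0.60 if 10-30% are lost on placebo only, and falls to 0.36-0.28 if they are lost on secukinumab only. These figures rest on the planned event rates, on an assumed share, and on every such failure becoming a non-loser. For lack-of-efficacy drop-outs the last assumption overstates the effect, since some draws will show loss.

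This deserves correction because the stated derivation gives an inconsistent result. It does not call the primary result into question.

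**What to change.** In SAP 1.9.4.2:

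1. State that in every imputed data set, time to loss is the earliest of PASI-based loss, first psoriasis medication and lack-of-efficacy drop-out, at the times given in 1.9.4. The event times fed to the Cox, log-rank, Wilcoxon and Kaplan-Meier steps should follow this rule.
2. State that MI replaces only the censoring of otherwise missing PASI, and reword the opening sentence, which names non-responder imputation as the method replaced.
3. Apply the same to loss of IGA 0 or 1 if MI is used there.

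If the PASI-only derivation is intended, say so and declare that the analysis targets a different estimand, so that it is not read as a check on missing data alone.

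Setting PASI after first psoriasis medication to missing before imputation is optional. It would keep on-medication values out of the imputation model, but the documents do not require it.

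The cost is a few lines of SAP text and code, with no new data.

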For loss of PASI 75 response, between-treatment differences will be evaluated using a logrank test, stratified by geographical region and body weight stratum, to compare the survival functions between secukinumab treatment groups versus placebo. The hazard ratios for these comparisons for loss of PASI 75 response and their corresponding 95% confidence intervals will be computed using a stratified Cox proportional hazards regression model with treatment group, core study and baseline PASI of core study and baseline PASI of extension study as explanatory variable and stratified by geographical region and body weight stratum.

Kaplan-Meier estimates including 95% confidence intervals for cumulative rate of subjects losing PASI 75 response will be calculated for each treatment group.

The number of subjects with loss of PASI 75 response, number of subjects in the analysis set, estimate of cumulative rate during RW period, median event time, and its estimated standard

Novartis	Confidential	Page 37
RAP Module 3	9-Apr-2018 (1:15)	Secukinumab / AIN457A2302E1

error, as estimable will be provided for each treatment group. In addition, for pre-specified time intervals (e.g., 4-week intervals) the following will be presented:

[figure not shown]
- for each treatment group and time interval: subjects at risk, subjects with loss of PASI 75 response, subjects with loss of PASI 75 response divided by subjects at risk, cumulative subjects with event and cumulative event probability including 95% confidence interval.
- for treatment comparisons the log-rank test and Wilcoxon test as well as the hazard ratio derived via Cox regression.

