ODS LISTING CLOSE; ODS OUTPUT ParameterEstimates=<results>; PROC MIANALYZE PARMS=<lgparms>; BY comp; MODELEFFECTS LogHR; RUN; ODS LISTING;

DATA <results2>; SET <results>; or=EXP(estimate); lowercl=EXP(LCLmean); uppercl=EXP(UCLmean); KEEP <By-variables> or lowercl uppercl probt; RUN;

- 1. **Cumulative Probabilities and CI:** Use log(-log(x))-transformed estimates for the survival function and their associated standard errors for each imputed data set and combine the results using Rubin's rules (PROC MIANALYZE). The transformation is done to ensure that resulting confidence intervals only include values between 0 and 1.
  - 1. Then back-transform combined estimates and associated CI intervals and calculate the 'cumulative' quantities.
  - 2. Calculate the mean across all imputed data sets for the columns: "subj. at risk" / "subj. with event" / "subj. with event/at risk"/ "cum. subj. with event", round them to the nearest integers as these will generally be non-integers.

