# T\_SURVIVAL=log(-log(SURVIVAL)); T\_STDERR= STDERR/(SURVIVAL\*log(SURVIVAL))

run;

4. Use the data set OUTSURV1 as input for PROC MIANALYZE to combine the results for T\_SURVIVAL and T\_STDERR based on the multiply imputed data sets. As we have two strata and different time intervals, we combine the estimates separately for each combination =strata \* time interval.

```
ods output ParameterEstimates=Survival_MI;
proc mianalyze data=outsurv1;
by combination;
modeleffects T_Survival;
stderr T_STDERR;
run;
```

5. Back-transform the combined survival estimates to the original scale and calculate the cumulative probabilities and associated CIs

```
data Survival_MI2;
set Survival_MI;
MI_survival=exp(-exp(Estimate));
LCL=(MI_survival)^exp(quantile('NORMAL',.975)*STDERR);
UCL=(MI_survival)^exp(-quantile('NORMAL',.975)*STDERR);
MI_cumulative= 1-MI_survival;
LCL_cum=1-UCL;
UCL_cum=1-LCL;
```

run;

**p-values from Log-rank and Wilcoxon tests:** Use transformed estimates for the Log-rank and Wilcoxon test statistics and their associated standard errors for each imputed data set using the Wilson-Hilferty transformation (Wilson & Hilferty, 1931; Goria, 1992) and combine the results using Rubin's rules (PROC MIANALYZE).

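### SAP 1.9.4.2 rounds an interval event proportion to a whole number in the multiple-imputation table and gives the log(-log) standard error the wrong sign

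*SAP*

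**What the plan says.** SAP 1.9.2 sets out the time-to-event table for loss of PASI 75 response: "for pre-specified time intervals (e.g., 4-week intervals) the following will be presented". The columns listed for each treatment group include "subjects at risk, subjects with loss of PASI 75 response, subjects with loss of PASI 75 response divided by subjects at risk", followed by cumulative subjects with event and the cumulative event probability with a 95% confidence interval.

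SAP 1.9.4.2 says how to fill that table from the 100 imputed data sets. The cumulative probabilities are pooled on the log(-log) scale. Four other columns are averaged over the imputations: at risk, with event, with event over at risk, and cumulative with event. The rounding instruction reads "subj. with event/at risk'/ 'cum. subj. with event', round them to the nearest integers". It covers all four, and no other part of the SAP exempts the ratio or gives it a number of decimals.

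For the pooled probabilities, the steps begin "Run PROC LIFETEST for each imputed data set and store estimates for the survivor function (SURVIVAL) and the associated standard errors (STDERR". They then define the transformed standard error as `STDERR` divided by the product of `SURVIVAL` and `log(SURVIVAL)`, with no minus sign or absolute value. The definition appears twice, once in the list of steps and once in the code. The result goes to PROC MIANALYZE through "stderr T_STDERR".

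**The concern.** Integer rounding makes sense for an averaged count, which is a whole number in each imputed data set. It does not make sense for a quantity defined as "subjects with loss of PASI 75 response divided by subjects at risk". That ratio lies between 0 and 1, and any value below 0.5 becomes 0. A programmer who follows the text literally would print a column of zeros beside non-zero event counts. One who quietly corrects it would depart from the SAP.

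The second fault is in the same block. Since log S is negative for 0 < S < 1, the stated formula gives a negative standard error. By the delta method, the standard error of log(-log S) is SE(S) / |S log S|. The SAP handles the same sign issue correctly a little earlier: when it recovers the standard error of the log hazard ratio from the Wald lower limit, it divides by minus the normal quantile, which gives a positive value.

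**Working it through.** **Inputs**
- SAP 1.11 and Protocol 9.7: 10% loss on secukinumab and 23% on placebo; 276 and 138 subjects; one-sided 2.5%; more than 90% power with about 400 subjects.
- Protocol 3.3 (text with Figure 3-3): about 10% lost per 4 weeks off treatment; 33.3% at 12 weeks; around 40% expected at 16 weeks.
- SAP 1.9.4.2: 100 imputations; the sample code runs from Week 52 to Week 68, which is four 4-week intervals.

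**The plan's own figure.** The plan states no value for the ratio column. Its power statement can be reproduced, which confirms that 10% and 23% are cumulative rates. HR = ln 0.90 / ln 0.77 = 0.403. Events at N = 400 are 266.7 × 0.10 + 133.3 × 0.23 = 57.3. Schoenfeld power is Φ(√(57.3 × 2/9) × |ln 0.403| − 1.96) = 90.0%.

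**Interval ratio.** With a constant hazard, a cumulative loss c over k intervals gives 1 − (1 − c)^(1/k) per interval.

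| Rate used | Per 4 weeks | Rounded as proportion | Rounded as percentage |
|---|---|---|---|
| 10% over 4 intervals | 0.026 | 0 | 3% |
| 23% over 4 intervals | 0.063 | 0 | 6% |
| 10% per interval | 0.10 | 0 | 10% |
| 40% over 4 intervals | 0.120 | 0 | 12% |
| 33.3% over 3 intervals | 0.126 | 0 | 13% |

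The zeros do not depend on even spacing. Apart from censoring and sampling variation, the ratio in any one interval cannot exceed the cumulative loss by Week 68. With at most 40% lost, it stays below 0.5 even if every loss fell in a single interval. In a simulation with 138 on placebo, no interval in Weeks 52 to 68 reached one half at rates of 2.6% to 12%.

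**The neighbouring columns.** In the first interval, the counts would be 276 × 0.026 = about 7 events on secukinumab and 138 × 0.063 = about 9 on placebo. These print correctly as whole numbers.

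**Standard error.** With SE(S) = √(S(1 − S)/n) at Week 68:
- Secukinumab: S = 0.90, n = 276, SE = 0.0181. Then 0.0181 / (0.90 × ln 0.90) = 0.0181 / (−0.0948) = about −0.190.
- Placebo: S = 0.77, n = 138, SE = 0.0358. Then 0.0358 / (0.77 × ln 0.77) = 0.0358 / (−0.2013) = −0.178.

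The correct values are +0.190 and +0.178. To see the effect on pooling, 100 estimates were simulated around S = 0.77, with an assumed between-imputation SD of 0.01 and n = 138. They were combined by Rubin's rules, once with negative and once with positive inputs. Both gave a pooled standard error of 0.185 and a survival interval of 0.689 to 0.835.

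**The case against.** The strongest reply is that the intent is plain. The reason given for rounding, that the averages will usually not be whole numbers, fits only the counts, and a dry run would expose the problem. That explains how the wording arose. It does not remove the instruction, which is the programming specification.

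Three other replies stand and limit the size of the point.
- The zeros assume that the ratio is displayed as a proportion. SAP 1.9.2 gives no format for this column, and elsewhere in that section it promises a number and percentage of subjects with loss. As a percentage, the arms would still separate.
- The table is supportive. SAP 1.1, Table 1-9 and 1.9.2 say that the Week 68 primary analysis is not repeated in the final analysis, and Table 1-14 bases the time to loss on observed data. Section 1.9.4.2 nevertheless keeps multiple imputation for loss of PASI 75, so the table may still be produced.
- The sign of the standard error has no demonstrated effect, because variances are pooled.

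A reader might infer that the table would show no loss of response in either arm. It would not: the event counts and the cumulative probability with its interval sit in the same table and are not damaged. A reader might also infer that the negative standard error swaps the confidence limits or causes the zeros. If a value of −0.178 went straight into the back-transformation, the limits would indeed swap (0.832 and 0.690). But the SAP code takes the standard error there from the pooled output, and the rounding step does not use it at all.

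**Conclusion.** The point holds as a minor specification error with two parts.

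First, as written, the ratio column would read 0 for Weeks 52 to 68 at every loss rate the documents give, provided it is shown as a proportion. Shown as a percentage at the planning rates, it would read about 3% against 6%. The finding is confined to that window. If the table ran to Week 156 (26 intervals), late intervals with few at risk could round to 1 instead. With 138 on placebo, the simulated chance of at least one such interval is 0 at 6.3% per interval, about 1% at 10% and about 10% at 12%.

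Second, the transformed standard error has the wrong sign for 0 < S < 1. Under Rubin's rules the pooled interval should be unchanged. The documents do not cover how the software treats a negative input, and nothing is claimed about that.

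The hazard ratio, the log-rank and Wilcoxon tests and the cumulative probabilities do not use the rounded column. No inferential conclusion of the trial depends on either fault.

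**What to change.** In SAP 1.9.4.2, limit the integer rounding to the three count columns. Report the mean ratio as a proportion to three decimals or as a percentage to one decimal, and state which. In both places where the transformed standard error is defined, write `T_STDERR = STDERR/ABS(SURVIVAL*log(SURVIVAL))`.

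The cost is about two lines of SAP wording and code. No data, design element or other analysis changes.
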